Section 1: Administrative information

1.a. Title

Statistical analysis plan for Predicting, Understanding, and Speeding Recovery after Total Joint Replacement; a Randomized, Controlled Clinical Trial.

1.b. Trial registration

Trial Registration: NCT02685735

2. SAP version

Version: 2.1 Date: February 6, 2023

3. Protocol Version

This document has been written based on information contained in the study protocol version 7.0, dated March 20, 2020.

4. SAP Revisions

Protocol version	Updated SAP version no.	Section number changed	Description and reason for change	Date changed
7.0	2.0	Section 6	Details provided after data acquisition and before unblinding	May 21, 2022
7.0	2.1	Sections 2 and 6	Corrected primary analysis to utilize resting pupil diameter rather than its response to pain as proposed in the NIH funding and protocol documents.	Feb 6, 2023
7.0	2.2	Section 6	Corrected the primary analysis to remove adjustment for baseline pain and in secondary analyses to remove adjustment for baseline activity, disability score, and opioid self administration.	April 26, 2023

5. Roles and Responsibilities – non-signatory names and contribution

[name].
Professor of Anesthesiology
Wake Forest School of Medicine
Winston-Salem, NC
Role: Chief investigator

[name].
Associate Professor of Anesthesiology
Massachusetts General Hospital
Boston, MA
Role: Co-investigator and Senior Statistician

6.a. Roles and Responsibility – signature of the person writing the SAP

[name].
Chief Investigator

April 26, 2013
Date

6.b. *Roles and Responsibility – signature of senior statistician responsible*

[name].
Co-Investigator & Senior Statistician

April 26, 2013

Date

Section 2: Introduction

7. *Background and Rationale*

People recover from pain after major surgery with very different speeds. In rats, recovery from hypersensitivity after major surgery also exhibits large variability, some of which is accounted for by individual differences in pain-induced activation of the locus coeruleus (LC) resulting in central norepinephrine release that dampens sensitization of pain circuits. Gabapentin alters LC coeruleus tonic activity in animals. We designed a study to assess, via pupillometry, LC tonic activity and responsiveness to pain prior to surgery in patients scheduled for lower extremity total joint arthroplasty and to test whether tonic activity and responsiveness to pain modulate the speed of recovery and efficacy of gabapentin to alter recovery from postoperative pain.

8. *Objectives*

The objective of this research study is to better understand patterns of recovery after total hip arthroplasty (THA) and total knee arthroplasty (TKA). The study will evaluate how pain, pupil diameter as a measure of LC activity and cognitive (i.e., thinking style) determine patterns of recovery, and the study will evaluate the efficacy of gabapentin versus placebo for improving recovery after surgery.

Research hypothesis: The null hypothesis (H_0) is that modeled trajectory of change in pain intensity report after THA and TKA does not differ between oral gabapentin and placebo in a manner dependent on its interaction with preferred cognitive style and pre-surgery pupil resting diameter. The alternative hypothesis (H_1) is that there is a difference between the two groups which is dependent on these interactions. The null hypothesis will be tested through contrasting the fit of a null model (m_0), with only change parameters and prognostic covariates, and the full model (m_1), which includes all of the predictors in null model with the addition of randomized treatment group, cognitive style, resting pupil diameter, and all two and three-way interactions. The difference in fit will be evaluated using a likelihood ratio test, as further described below.

$$H_0: -2 * (\loglik[m_0] - \loglik[m_1]) = 0$$

$$H_1: -2 * (\loglik[m_0] - \loglik[m_1]) > 0$$

Study objective: The primary objective is to determine the effectiveness of oral gabapentin to speed recovery from pain, as measured by growth curve modeling, after THA or TKA and how this effectiveness is modified by preferred cognitive style and pre-surgery resting pupil diameter.

Secondary objectives are planned to explore the role of these factors interact to predict other outcomes from surgery, including speed of gain in activity, assessed by actigraphy, speed recovery from self-assessed disability, and time to cessation of opioid use; to explore whether change in pupil diameter to acute experimental pain explains additional variance in a 4-way interaction compared to the 3-way interaction in the primary analysis.

Section 3: Trial Methods

9. Trial design

[figure not shown]
The trial is a two-center, randomized, double-blinded, parallel-group, placebo-controlled trial. Treatment allocation is a 1:1 ratio. Patients are randomized to either gabapentin or placebo control.

10. Randomization

A computer-generated randomization using a 1:1 allocation ratio in permuted blocks of 8 will be developed by the study statistician uninvolved with data collection and administered by the research pharmacist at Wake Forest School of Medicine. The 'blockrand' package in R will be used by the study statistician. The randomization will be stratified based on study recruitment site, concurrent use of a serotonin-norepinephrine reuptake inhibitor, and chronic low- or high-dose opioid therapy. Allocation will be conducted by the research pharmacist and will occur after consent and completion of the first visit. At all times, the allocation assignment will be concealed from the study coordinator and other investigators who manage participant recruitment and follow-up. Allocation concealment is maintained using a centralized pharmacy administration of study drug. Both study agents are designed to look identical to each other to maintain blinding.

11. Sample size

To calculate the statistical power for our analytical strategies, we simulated scenarios for which we instilled known relationships between the random effects of change models as well as a range of predictors of those parameters that were themselves correlated. A sample size of 250 was to determine to provide substantial power (> 90%) to detect clinically significant differences between a null model versus a demographic/perioperative + psychosocial predictors model using a likelihood ratio test. An example of the expected differences is displayed (left) that illustrates a three-way interaction between treatment (Placebo vs Gabapentin), cognitive-affective style (Optimist vs Catastrophizing), and pupil size (Low, Mid, High).

12. Framework

Superiority testing will be used to examine difference between the effect of treatment alone on the change process in pain after surgery and the effect of treatment as interacting with preferred cognitive style and pre-surgery pupil responses to painful stimuli.

13a. Information on interim analyses

There are no planned interim analyses.

13b. Any planned adjustment of the significance level due to interim analysis

None.

13c. *Details of guidelines for stopping a trial early*

There is no plan to stop the trial early aside from recommendations based on unanticipated serious adverse events by the DSMB.

14. *Timing of final analysis*

Table 1. Timing of study measures

Study period	Screen	Baseline	In hospital	Daily diaries	Follow up 1	Follow up 2	Phone	Orthopaedic clinic visits
Visit number	0	Visit 1			Visit 2	Visit 3		
Week		-4 to -2*	0-3 days	0-8	8	26	12,16,20,52	2, 6, 12-16, 26, 52
Informed consent		X						
Demographic		X						
Medical/surgical history		X						
Questionnaires		X			X	X		
Pain testing & pupillometry		X						
Randomisation		X						
Study drug dispensing		X						
In hospital pain/medication data & disposition			X					
Daily diary & accelerometry		X		X				
Phone assessment of pain, medication use, function							X	
Joint function								X

*Study medication begins at -2 weeks and continues until 3 weeks after surgery

Final analysis of the gabapentin vs placebo comparison with and without inclusion of interactions with preferred cognitive style and pre-surgery pupil responses to pain will take place when all patients have completed the 12-month follow-up and data for the primary endpoint have been cleaned, which occurred in May 2022. Results were anticipated to be posted by Jan, 2023, but complexities associated with generation of a novel psychologic construct from the final dataset and defining parameters for pupil assessment prevented completion of the primary analysis until Mar, 2023.

15. *Timing of outcome assessments*

The schedule of study procedures is provided in the protocol and summarized in the table below.

Section 4: Statistical Principles

16. *Level of statistical significance*

All applicable statistical tests will be 2-sided and will be performed using a 5% significance level.

17. *Adjusting for multiplicity*

The primary analysis involves a single model-based inference that will be interpreted at the 5% threshold of statistical significance. If the primary analysis is significant, each main factor, all two way interactions, and the three way interactions will be evaluated and each will be interpreted at the 5% level of significance with no adjustments made for multiplicity.

18. *Confidence intervals*

All confidence intervals presented will be 95% and two-sided.

19a. *Definition of adherence to the intervention and how it is assessed*

Compliance is assessed based on the number of daily diary entries after hospital discharge. It is defined as:

$$\% \text{ compliance} = (\text{number of entries}/\text{number of days entries were to be completed}) * 100\%$$

19b. *How adherence will be presented*

The number and % of participants completing more than 80% of the daily diaries after surgery will be provided by treatment group in a table. All available data will be included in the analysis from the intention to treat sample.

19c. *Definition of protocol deviation*

The following are pre-defined major protocol violations with a direct bearing on the primary outcome:

- 1) Surgery during the primary outcome assessment period (first 8 weeks after surgery)

19d. *Description of which protocol deviations will be summarized*

Protocol deviations are classified prior to unblinding of treatment. The number (and percentage) of patients with major and minor protocol deviations will be summarized by treatment group with details of type of deviation provided. The patients that are included in the ITT analysis data set will be used as the denominator to calculate the percentages. No formal statistical testing will be undertaken.

20. *Analysis population*

The intention-to-treat population will include all randomized patients who received study drug and provided at least one pain score after the day of surgery.

Section 5. Trial Population

21. *Screening data*

Enrollment: The dates of recruitment, the number of patients screened, the number of patients recruited, the number of screened patients not recruited, and the reason for non-recruitment will be reported as part of the CONSORT diagram.

22. *Eligibility criteria*

Inclusion and exclusion criteria are provided in the protocol. The number of ineligible patients randomized, if any, will be reported, with reasons for ineligibility

23. *Information to be reported in the CONSORT flow diagram*

A CONSORT flow diagram (appendix A) will be used to summarize the number of patients who were:

- assessed for eligibility at screening
 - eligible at screening
 - ineligible at screening*
 - eligible and randomized
 - eligible but not randomized*
 - received the randomized allocation
 - did not receive the randomized allocation*
 - lost to follow-up*
 - discontinued the intervention*
 - randomized and included in the primary analysis
- *reasons will be provided for post randomization exclusions.

24a. *Description of level of withdrawal*

The level of consent withdrawal will be tabulated (classified as “consent to continue follow-up and data collection” “consent to continue data collection only”, “complete – no further follow-up or data collection”).

24b. *Timing of withdrawal/lost to follow up data*

This will be presented in CONSORT diagram format rather than as a table, with numbers and reasons for withdrawal and/or exclusion from analysis given at each stage

24c. *Reasons for withdrawal/lost to follow up data*

The numbers (with reasons, if available) of losses to follow-up (drop-outs and withdrawals) over the course of the trial will be summarized by treatment arm.

25a. *List of baseline characteristics to be summarized*

Patients will be described with respect to age, sex, race, ethnicity, medications, number of painful conditions excepting the hip and their locations, cognitive – optimism cognitive construct generated from questionnaires, baseline pain from the daily diaries prior to surgery, and surgical approach (anterior vs posterior).

25b. *How baseline characteristics will be described*

Categorical data will be summarized by numbers and percentages. Continuous data will be summarized by mean, SD and range if data are normal and median, IQR and range if data are skewed. Minimum and maximum values will also be presented for continuous data. Tests of statistical significance will not be undertaken for baseline characteristics; rather the clinical importance of any imbalance will be noted.

Section 6: Analysis

26. *Outcomes and timings*

Primary outcome: Worst pain intensity measured using a 0 to 10 numerical rating scale on a daily diary. Measurements will be obtained each evening from day 0 (surgery) to day 56 after surgery. The pain measurements will be evaluated in a statistical model using an intercept (i.e., immediate pain after surgery) and slope (i.e., rate of change of pain during the observation period).

Secondary outcomes: Daily measurements such as physical activity, as measured via actigraphy, disability, as measured by daily diaries and weekly WHODAS 2.0 scores, and opioid self-administration, as measured by daily diaries will be collected from day 0 (surgery) to day 56 after surgery. Questionnaire and cognitive game data will be assessed at baseline and follow-up. Validated scoring systems from the individual items will be used to score each questionnaire or measure. These outcomes will not be used in the primary analysis.

27a. *Analysis methods to be used and*

27b. *Adjustments for covariates*

Primary analysis:

Overview

The primary analysis will model trajectory of recovery of daily worst pain ratings and examine several sources of influence on this recovery. Sometimes referred to as mixed-effects models, or hierarchical linear models, growth curve modeling allows specification of a change trajectory that is unique to each individual. The nature of the common form of changes in daily pain will be modeled using a curvilinear form (e.g., polynomial regression). Through the use of fixed and random effects, variations in intercepts (i.e., levels of pain on day of discharge) and slopes (i.e., change in daily pain over time) can be examined using the pre-specified influences outlined below. To model individual pain trajectories, several model form candidates will be examined with the best fit determined using a Bayesian Information Criterion. These model forms will include linear, quadratic, cubic, and log(time), and each of these model candidates will be employed that reflect a fundamental change in trajectory that occurs during the observation period. Based on preliminary data it is highly likely that a log(time) form will be chosen.^{1,2}

To examine the proposed hypotheses, several key sets of predictors will be specified including patient characteristics, operative characteristics, cognitive style, randomized treatment assignment, and pre-operative pupil diameter response. Each of these predictors are described below:

Patient characteristics: To adjust the associations for individual age and sex will be entered into the model.

Operative characteristics: To adjust the associations for any subtle differences in medical care, study site, and surgery type (hip or knee arthroplasty) will be entered into the model.

Cognitive style: Multidimensional scaling of the pre-operative questionnaires will be conducted to create a unidimensional scale that represents a broader spectrum of cognitive style that ranges from optimism/acceptance of pain to catastrophizing. This novel predictor will be examined for reliability and correlations with the original scales. If insufficient reliability ($\alpha < 0.70$) or construct validity ($r < |0.40|$) with the original scales cannot be obtained, the analysis will proceed using the originally scaled catastrophizing predictor.

Pupil diameter: Pupil recordings will be conditioned to remove artifacts (e.g., blinks), saccades, and deviations from central gaze that might bias recordings. A response window with appropriate lag reflecting delayed onset of pupil response due to physiological delays will be used to define change in diameter to each stimulus as previously reported.¹⁷ Two pupil measurements will be estimated from the session data, the mean pupil diameter during baseline (i.e., pre-stimulus) and the modeled response to pupil to 50-degree stimulus.

Gabapentin: Randomized treatment assignment of either gabapentin or placebo will be a fundamental predictor of trajectory.

These individual predictors sets will then be used to test the primary hypothesis that gabapentin alters time course of recovery after arthroplasty in a manner dependent on its interaction with preferred cognitive style and pre-surgery pupil diameter. The primary statistical inference will be the difference in the likelihood ratio between two nested models using a chi-square test with K degrees of freedom (i.e., K being the difference in the number of parameters between the two models). The first model (i.e., null model) will consist of the pain trajectory model with the addition of patient characteristics and operative characteristics. The second nested model will add medication assignment (gabapentin versus placebo), cognitive style (catastrophizing \leftrightarrow optimism latent score), and resting pupil diameter, and all two-way interactions and three-way interaction between these 3 predictors (i.e., 3 two-way, and 1 three-way interaction for both intercept and slope parameters) from the first nested model. This approach allows a single likelihood ratio test of the primary hypothesis and will be interpreted using a two-tailed hypothesis test using $p < 0.05$. A statistically significant difference in the likelihood ratio test will be interpreted as evidence to support the primary hypothesis in that the interaction of these predictors impacts some aspect of the change process beyond that of the basic model. We have planned several sensitivity analyses using multiple imputation to account for missing data.

Several exploratory secondary analyses of the data set:

1. Trajectories for daily activity, as measured via actigraphy, disability, as measured by daily diaries and weekly WHODAS 2.0 scores, and opioid self-administration, as measured by daily diaries, will be analyzed using a similar approach. As noted, other questionnaire and cognitive game scores will be described for the two groups but not analyzed or entered as covariates for the purpose of the primary analysis and publication. Changes in questionnaire data will be evaluated using the generalized linear model regressing follow-up score on baseline score and medication group assignment.

2. The contribution of pupil diameter change in response to acute preoperative pain testing to prediction of trajectory of change in postoperative pain intensity rating will be assessed. This will be performed in the same manner as the primary analysis. In addition, a 4 way-interaction test using the same approach as in the primary analysis will be used by included both pupil diameter at rest and its response to preoperative acute pain stimuli.

3. Development and internally validation a predictive model for recovery from pain from the full battery of preoperative questionnaires and application of item response theory to create a much smaller set of questions with retained predictive value for subsequent testing as a practical tool.

4. Modeling recovery of function from the World Health Organization Disability Assessment Score 2.0 (WHODAS 2.0), Western Ontario and McMaster Universities Osteoarthritis Index (WOMAC) and daily activity level as assessed using actigraphy in order to assess their relationships and those between these functional measures and daily pain, including lead-lag and influence of days of physical therapy, during recovery from physical therapy after lower extremity major total joint arthroplasty.

5. Examining the influence of anesthetic technique (general anesthesia, regional anesthesia via single injection regional anesthesia with sustained catheter infusion) on perioperative acute pain and pain and functional recovery over the subsequent two months.

6. Exploring biomarkers for stress and noradrenergic functioning by exploring the relationship between preoperative patient characteristics, including psychophysical responses to pain processing and CSF concentrations of norepinephrine and markers associated with stress.

27c. Methods to be used for assumptions to be checked for statistical methods for primary and secondary analyses

The assumptions underlying parametric modeling will be evaluated using regression diagnostic procedures and histograms of residuals.

27d. Alternative methods to be used if distributional assumptions do not hold for primary and secondary analyses

If necessary, the primary outcome distribution will be log transformed to satisfy assumptions. For secondary outcomes, the generalized linear model allows the specification of an array of distributions (e.g., normal, binomial, gamma) with corresponding link functions (e.g., log).

27e. Planned sensitivity analyses

Four sensitivity analyses will be performed to evaluate the robustness of the trajectory analysis to the primary and secondary analyses. These are to include multiple imputation for missing data, to include baseline measures of primary and secondary outcomes as predictors in the trajectory models, to include monthly through 6 months and the 12-month daily diary data and to include patient race and surgeon as other causes of variability in trajectory in the primary analysis.

27f. Planned subgroup analyses

No subgroup analyses are planned.

28. Missing data – reporting and assumptions/statistical methods to handle missing data

Multiple imputation will be used to account for embedded missing data in daily diary entries. The autocorrelation of each time-series for each individual along with baseline predictors will be used in conjunction with the MICE algorithm to estimate $m = 20$ imputations. These imputations will then be re-analyzed using the primary model with Rubin's rules used to pool the estimates of model parameters.

29. *Details of any additional statistical analyses required e.g., complier-average causal effect analysis.*

None

30. *Harms*

The number (and percentage) of patients experiencing each AE/SAE will be presented for each treatment arm categorized by severity. For each patient, only the maximum severity experienced of each type of AE will be displayed. The number (and percentage) of occurrences of each AE/SAE will also be presented for each treatment arm. No formal statistical testing will be undertaken

31. *Statistical Software*

The analysis will be carried out using R version 4.1.2

32. *References*

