Appendix

SAP 2.1

The SAP was amended on Feb 6, 2023 to correct an error in the primary analysis in SAP 2.0 which stated that pre-surgery pupil response to acute experimental pain would be entered into a three way interaction with study drug and preferred cognitive style to predict modeled recovery from pain after lower extremity total joint arthroplasty. As stated in the NIH application which funded the research, the IRB approved protocol for the study and its analysis, and the ClinicalTrials.gov registration, the primary analysis was stated to use pre-operative resting pupil diameter rather than its response to pain. The error in the SAP was observed prior to performing the primary analysis and is described in this amendment.

Addition of pre-surgery pupil response to acute experimental pain as a 4th interacting factor was inferred in the grant application and protocol and the SAP is amended to include this as a pre-planned secondary analyses from this extensive dataset, in addition to creating a unique subset of questionnaire questions to predict postoperative pain intensity trajectory, assessing the day to day time relationship between pain and disability during recovery, the role of anesthetic technique in long term recovery, and interrogating various biomarkers for speed of trajectory of recovery after surgery.

SAP 2.2

The SAP was amended a second time on April 26, 2023 to correct an error in the primary and secondary analyses to remove the statements that modeled trajectory of change in outcome measures for each analysis (pain in the primary; daily steps, disability scores, and opioid use in the secondaries) would be adjusted for preoperative values of these measures. Such adjustments were not included in either the IRB approved protocol nor the NIH application which funded the study and its analysis.

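### Section 8 sets time to stopping opioids as a secondary objective, but the SAP analyses only the course of daily opioid use

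*SAP*

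**What the plan says.** Section 8 (Objectives) says that the secondary objectives will explore how the study factors predict other recovery outcomes. It names gain in activity, then "speed recovery from self-assessed disability, and time to cessation of opioid use".

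Section 26 (Outcomes and timings) describes the opioid outcome only as a daily measurement: "opioid self-administration, as measured by daily diaries will be collected from day 0 (surgery) to day 56 after surgery". It does not define a stopping event.

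Section 27a/27b, item 1 of the exploratory secondary analyses, plans trajectories for activity, disability and opioid use. For the last of these, "opioid self-administration, as measured by daily diaries, will be analyzed using a similar approach". The approach referred to is that of the primary analysis, where "growth curve modeling allows specification of a change trajectory that is unique to each individual", with intercept and slope terms and a likelihood ratio test between nested models.

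Section 27d adds that for secondary outcomes "the generalized linear model allows the specification of an array of distributions (e.g., normal, binomial, gamma", and so on, with matching link functions.

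The Appendix entry for SAP 2.2 lists the outcomes with modelled trajectories as "pain in the primary; daily steps, disability scores, and opioid use in the secondaries".

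**The concern.** An objective about when patients stop opioids calls for an event, a time origin and a rule for patients who have not had the event when observation ends. A trajectory model describes something else: the level of daily use and how it changes. If the SAP is followed exactly, the trial will have a result on the course of opioid use and none on time to stopping, although Section 8 promises one.

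Two consequences follow. A difference in trajectory could be reported as a difference in how soon patients stop, which the model does not estimate. Or the gap could be filled at the reporting stage with a stopping rule chosen after the data are known. The second risk is practical here: the revision table in Section 4 records that SAP 2.0 was itself written after data acquisition, though before unblinding.

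**Working it through.** The SAP gives no figure to reproduce on this point. The check sets the objective, outcome definition and analysis side by side.

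| Objective (Section 8) | Type of quantity | Analysis (Section 27 item 1) | Match |
|---|---|---|---|
| Gain in activity | Speed | Trajectory | Yes |
| Recovery from disability | Speed | Trajectory | Yes |
| Stopping opioids | Event time | Trajectory of daily use | No |

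**What an event-time analysis would need, and whether the SAP has it**

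- *Event definition:* absent. Stopping is mentioned only in Section 8. Nothing says how many opioid-free days count or what happens if use resumes.
- *Patients using opioids before surgery:* not addressed. Section 10 stratifies randomisation by "chronic low- or high-dose opioid therapy", so such patients are expected in the trial, and the meaning of stopping for them has to be stated.
- *Censoring:* absent. Section 28 imputes gaps within the diary series. That is not a rule for patients still using opioids at day 56 or whose diaries end earlier.
- *Method:* no survival or hazard model is named in Section 27 or 27d.
- *Later data:* Table 1 has a row "Phone assessment of pain, medication use, function" at weeks 12, 16, 20 and 52, and Section 27e plans a sensitivity analysis with later diary data. Neither is tied to stopping.

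**Why a trajectory does not supply the answer by itself**

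Take a straight-line decline for illustration, with daily use = a − b·t. It reaches zero at t = a/b, so the stopping time depends on starting level and slope together. The figures below are hypothetical.

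- Same stopping time, different slopes: a = 1 with b = 1/21, and a = 2 with b = 2/21, both reach zero on day 21. The slopes differ twofold.
- Same slope, different stopping times: with b = 1/21, a = 1 reaches zero on day 21 and a = 2 on day 42.

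Under a log(time) form, which Section 27 expects for pain, the curve a − b·log(t) reaches zero at t = exp(a/b), and the same point holds. A stopping time could be derived from a fitted curve, but the SAP neither says that it will be nor gives a threshold for doing so.

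**The case against.** The best defence is that Sections 26 and 27 and the Appendix all treat opioid use as a trajectory, so the phrase in Section 8 may be loose wording for recovery from opioid use. The analyses are also exploratory, and Section 27d leaves room for non-normal outcomes. A binomial model of daily use would at least show the probability of use falling over time. A discrete-time hazard model is itself a binomial model, so 27d does not rule one out.

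Much of this stands. It limits the importance of the point and makes rewording the objective a legitimate remedy. It does not make the sections agree. A binomial model becomes a hazard model only once the event is defined and the data are restricted to days at risk, and the SAP does neither.

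Three stronger readings are tempting and are not supported:

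- *That opioid use goes unanalysed.* It is analysed; only time to stopping is not.
- *That the SAP commits to a normal-errors model for opioid use.* It says the approach is similar to that for pain, and 27d allows other distributions.
- *That the trajectory model must fit badly because most diary days are zero.* The share of zeros depends on an assumed stopping day and on no resumption. With last use on day 14, 21, 28 or 42, zeros would fill 42, 35, 28 or 14 of the 57 diary days (74%, 61%, 49% or 25%). The SAP supports none of these days, nor the assumption that use never resumes.

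**Conclusion.** The mismatch is real. Section 8 names an event time, while Sections 26 and 27 define and analyse the course of daily use. Of the three recovery outcomes named together in Section 8, this is the only one whose planned analysis targets a different quantity.

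The conclusion rests on the SAP text alone. The protocol could define stopping, but the SAP would still state one quantity as its objective and plan the analysis of another. The impact is limited to the exploratory secondary analyses. The primary likelihood ratio test, the sample size and the multiplicity statement are unaffected. The SAP should be corrected, but the trial's main conclusion does not depend on it.

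**What to change.** Make Sections 8, 26 and 27 agree in one of two ways.

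1. **If an event-time result is intended**, add to Section 27 item 1 an analysis of time from surgery to stopping opioids, taken from the daily diaries.
   - Define the event beforehand, including how resumption is handled and what stopping means for patients on chronic preoperative opioids. Stratifying by that factor does not define the event for them.
   - Censor at day 56 or the last diary.
   - Use a Cox or discrete-time hazard model with the primary model's covariates and the treatment × cognitive style × resting pupil terms, stratified by the preoperative opioid stratum.
   - Keep the trajectory analysis as supportive.
2. **If it is not intended**, reword the Section 8 objective as the trajectory of opioid self-administration, and draw no conclusion about time to stopping.

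Either way, date the change in the revision table, and label it post hoc if it is made after unblinding. The second route costs one sentence. The first costs an event definition and one extra exploratory model on diary data already collected.
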